PtdCho	phosphatidylcholine
PEMT	phosphatidylethanolamine- N -methyltransferase
QC	quality control
RDI	recommended daily intake
SAE	serious adverse event
SNP	single nucleotide polymorphisms
TPN	total parenteral nutrition
UL	upper limit
UP	unexpected problem
VIP	variable importance to projection

PROTOCOL SYNOPSIS

Study Title	Choline Nutritional Status: Development of a Biomarker Panel
Funder	NIH, Balchem
Clinical Phase	N/A
Study Rationale	Cho is an important nutrient, for which Adequate Intake and Reference Daily Intake values have been established, however Cho consumption is lower than recommended in most people, which can lead to liver and/or muscle dysfunction. Plasma Cho concentrations are a poor biomarker for choline status because it is homeostatically regulated. We have previously identified biomarkers that changed in people who became sick due to Cho depletion. We propose that a score for Cho status based on measurements of these markers can be used by clinicians and scientists to identify people who may be at risk of developing organ dysfunction due to Cho deficiency unless their Cho intake is increased.
Study Objective(s)	
Aim 1: Determine whether a Cho status score based on a panel of biomarkers correlates well with measures of Cho pool size as assessed using an isotope dilution method.
 
SubAim 1a: To test assumptions used in the choline isotope dilution method for estimating choline pool size, subjects will undergo MRS of Cho compound peaks in liver. Fatty liver will be assessed by MRI to compare to and validate the Fibroscan methodology.
 
SubAim 1b: Determine whether there are additional biomarkers from untargeted metabolomic profiling that, when added to the panel developed in Aim 1, are better at predicting Cho status in people.
 
SubAim 1c: Determine whether people with genetic polymorphisms (SNPs) known to increase risk for developing Cho deficiency-induced organ dysfunction are also more likely to have a worse Cho status score and a reduction in choline pool size assessed using isotope dilution.

Test Article(s) (If Applicable)	The experimental diets, delivering 100%, 50% (to be determined by a pilot study) and 25% of the recommended intake of Cho (in all forms) (550 mg Cho/70 kg body weight/d), are identical except for the bread that we offer (Cho in the bread will be varied to deliver the desired Cho above that delivered by the base 25% Cho diet as described previously (1)). On day 12 of a diet period, subjects will consume 250mg Cho in the form of Cho chloride (trimethyl-d9). We will confirm total Cho content of diets by LC-MS/MS analysis of samples of duplicate food portions as previously described (1).

Study Design	Healthy volunteers (n=50 males, 50 premenopausal females and 50 postmenopausal females; 30 additional subjects for dropout replacement), will be randomly assigned to an order of 2 week intervals of diets where they consume meals that we provide containing 100% of the recommended intake of Cho (550 mg Cho/day), 50% of the recommended intake of Cho (275 mg Cho), and 25% of the recommended intake of Cho (137.5 mg Cho) for 2 weeks each. Each dietary interval is followed by a minimum 2 week washout period. On day 12 of each diet period, subjects will consume a bolus of 250mg of Cho in the form of Cho chloride-(trimethyl-d9). Before this bolus, a plasma sample will be collected to measure baseline enrichment of Cho isotopes. At the end of each diet period, plasma and urine samples will be collected for biomarker assays and isotopic dilution estimation of Cho pool size, and we will perform transient elastography (Fibroscan) of liver to assess liver fat. (see Fig. 1, appendix).
Subject Population key criteria for Inclusion and Exclusion:	
Inclusion Criteria
 
 1. Subjects age 17 – 70 years 2. Male & female; representative of the Kannapolis-Charlotte metro area 
Exclusion Criteria
 
 1. Implantable devices, BMI > 32, smokers, pregnant or planning to become, allergies to food to be consumed, chronic systemic diseases, consuming Cho-containing supplements, consuming drugs or medications known to cause liver or muscle damage or to alter Cho metabolism (e.g. methotrexate). For MRI/MRS we will exclude claustrophobia, pacemaker, artificial heart valve, metal plate, pin, or other metal implant, intrauterine devices such as Copper-7 IUD, insulin or other drug pump, aneurysm clips, previous gunshot wound, cochlear implant, or other hearing device, employment history as a metal worker, permanent (tattoo) eye-liner.
Number Of Subjects	180
Study Duration	Each subject's participation will last 6 weeks and a few days. This does not include the washout period between the dietary arms (minimum of 2 weeks each). The entire study is expected to last 4 years.
Study Phases	(1) Screening : screening will take place in years 1-3 with the goal of consenting 50 subjects per year to complete the study.
Screening	
Study Treatment	(2) Intervention : the study will take place in years 1-3. Subjects will be placed on diets as described in the study design (figure 1, app).
Follow-Up	

(3) Follow-up: year 4 of the study will involve data analysis and interpretation, and writing of a manuscript for publication.

Efficacy Evaluations	
Expected Results and interpretation:
 
Our aim is to develop a panel of biomarkers and an algorithm for calculating a Cho status score that correlates well with measures of Cho pool size by isotope dilution. We will define the minimum set of biomarkers that provides >90% accuracy in predicting Cho pool size measured by isotopic dilution. We expect to see incremental declines in Cho status, as reflected in the panel of biomarkers. Results on the 100% diet should be similar to what we previously published. In the earlier studies, subjects were fed the 10% diet for a period of 2 to 7 weeks; in the proposed study, we feed 25%, 50%, and 100% (adequate intake) diets for two weeks (order randomly assigned) with 2 week washout periods in between. We expect that our results on the 25% & 50% diets will be less than those previously described; i.e. there will be smaller difference in the biomarkers than previously described. We expect that the 25% & 50% diets will show changes in Cho pool size and in biomarkers that fall between 100% and 10% values. Genotype will change the rate at which a diet treatment alters Cho pool size but will not affect whether our biomarker panel correlates with the pool size achieved. Thus, we do not have to power the study for genotype differences.

Pharmacokinetic Evaluations	N/A
Safety Evaluations	After each diet period a clinical chemistry panel will be run to assess potential liver and muscle damage. If any damage is noted after any of the dietary periods (liver damage = >1.5-fold increase in aspartate aminotransferase (AST) alanine transaminase (ALT) or muscle damage = >5-fold increase in creatine phosphokinase (CK)), affected subjects will follow the abnormal lab value protocol chart (See Appendix Figure 6). This will be reported to the IRB and the subject will be monitored and re-tested according to protocol and until AST/ALT and CK values return to normal.
Statistical And Analytic Plan	(Aim 1, SubAim 1a,1b). Unsupervised principal component analysis will first be used to examine the clustering of samples from the diet periods, and to ensure that the QC pool replicates center in the samples from which they were derived. Supervised Orthogonal Partial Least Squares Regression (OPLS-R) will then be used to identify a panel of biomarkers, assign weight to each biomarker, and calculate a composite score to predict choline pool size. We will analyze all of the samples using OPLS-R to identify a panel of biomarkers that predicts choline pool size universally for all three diet periods (healthy men, pre- and post-menopausal women). We will also consider performing the analysis for each diet period separately in case the universal panel does not provide high accuracy in prediction. Variable Importance to Projection (VIP) score will be calculated based on the OPLS weights and the variability explained in OPLS-R. Biomarkers with VIP>1.5 will be considered the most important biomarkers responsible for prediction.

Pathway analysis will be performed using GeneGo metacore (Thomson Reuters, <https://portal.genego.com>) and QIAGEN's Ingenuity Pathway Analysis (IPA®, QIAGEN Redwood City, www.qiagen.com/ingenuity).

DATA AND SAFETY MONITORING PLAN [name] (PI), [name] MD, and study physician, [name] will monitor subject data for safety continuously throughout the study and as new subjects are recruited.

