People need to have a source of Cho: Cho has several important functions. It is (i) a source of methyl-groups needed to make the primary methyl donor, S-adenosylmethionine; (ii) a part of the neurotransmitter acetylCho; and (iii) a component of the major phospholipids in membranes (phosphatidylCho (PtdCho) and sphingomyelin)

(13). The Cho derivative, PtdCho is a main constituent of very low density lipoproteins (VLDL) and is required for VLDL secretion and the export of fat from liver (14). Cho also is important for normal fetal development (15, 16).

Cho is a required nutrient and in 1998, an Adequate Intake (AI) and a Tolerable Upper Limit (UL) for Cho was established (17). In 2016, the US Food and Drug Administration (FDA) set a Recommended Daily Intake (RDI) for Cho based on the AIs as part of the new Nutrition Facts label for packaged foods (published in the Federal Register on May 27, 2016; FDA-2012-N-1210-0875, Federal Register Number:2016-11867). The AI/RDI varies by age and gender, but is 550 mg/d in adult men and 425 mg/d in adult women (more in pregnant and lactating women).

Dietary Cho intake varies over a 3-fold range: There is a wide variation in Cho intake in the diet; in several human cohorts, Cho intake varies by approximately 3-fold – the US National Health and Nutrition Examination Survey (NHANES 2009-2012) data show that only 11% of adult Americans achieve the Adequate Intake level of Cho, with mean intake being 300 mg/day (10%ile being 200 mg/d; 90%ile being 500 mg/d) (2). Similar ranges of intake were reported in the Framingham Offspring Study (18), the Atherosclerosis Risk In Communities study (19, 20) and the Nurse's Health Study (21). Intake of Cho is even lower in low-income countries such as Jamaica and The Gambia (22, 23).

[figure not shown]

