depletion was associated with abnormal renal function in animal models (62); a number of metabolites that accumulate in people with diminished renal function, including 3-carboxy-4-methyl-5-propyl-2-furanpropanoate (CMPF), hippurate and 3-indolepropionate also were significantly increased by Cho depletion in our study subjects (10). Cho is important for mitochondrial function (63, 64), and in our study, plasma concentrations of several acylcarnitines were increased, reflecting perturbed mitochondrial function (65). In addition, people with SNPs that increase susceptibility to Cho deficiency had > 50% increased concentrations of propionylcarnitine (10). Plasma concentrations of a number of amino acids and their metabolites increased in Cho depletion (glutamine, pyroglutamate, glycine, valine, glutamyl-valine, and leucine) (10). Finally, plasma concentrations of a number of metabolites released from dying cells (urate and pseudouridine) were elevated in Cho depleted subjects (10). The alterations associated with Cho depletion in most metabolites were at least partially corrected by Cho repletion (10).

When people were depleted of Cho they developed abnormal aspartate transaminase (AST; marker of liver damage) and creatine phosphokinase (CK; marker of muscle damage) activities in blood (24, 52). This occurs because Cho deficiency induces apoptosis in tissues (26, 66, 67). Development of fatty liver was also a marker for Cho depletion in people fed low Cho diets (24, 25, 52, 55). Previously, we used mass resonance imaging to quantitate the fatty liver that occurred with Cho depletion (24) but this method is expensive and we believe that other non-invasive methods can be used to assess fatty liver. Controlled Attenuation Parameter (CAP) is a new ultrasound-based technique to measure steatosis simultaneously with assessment of liver stiffness using transient elastography (TE); it has been used in research studies (68-72) and is being used in hepatology clinics (73, 74). The measures of organ dysfunction discussed above, could improve a panel of other biomarkers by providing information assessing likely organ effects associated with Cho depletion. Though we expect elevations in these markers, we do not anticipate clinically significant damage based on this study design (see Safety).

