1.3 Non-Clinical and Clinical Study Findings

There are no expected benefits to the subjects in the study.

Safety: Participants will remain on the above-noted experimental diets for the indicated time periods, or until they develop organ dysfunction associated with Cho deficiency (liver damage = >1.5-fold increase in aspartate aminotransferase (AST) or alanine aminotransferase (ALT), or muscle damage = >5-fold increase in creatine kinase (CK)). A clinical chemistry panel will be run at the beginning of the study (Screening) and at the beginning and end of each dietary period of the study. If they develop organ dysfunction at the end of any of the experimental diet periods, subjects will be monitored according to the protocol established for abnormal lab values (See Appendix Figure 6). We have extensive experience with these diet formulations (24, 52, 55) and have not observed clinically significant liver or muscle damage in individuals fed the 10% Cho diet for 2 weeks or less. After longer periods on a 10% Cho diet, clinically liver and muscle damage was noted, and reversed with 2 weeks of feeding 100% Cho diet. No other toxicity was observed after as long as 7 weeks on the 10% Cho diet (24, 52, 55). A urine pregnancy test will be performed on premenopausal women at the beginning and end of each dietary arm.

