3.1 Study Design

This is a crossover study wherein each subject will serve as their own control. Comparisons will be made between the low choline diet periods to the 100% choline diet at the beginning and end of the 6 weeks on the three dietary intervals (see Fig. 1, Appendix).

Screening: Before entry to the study the participants will be seen at the University of North Carolina Nutrition Research Institute Outpatient Clinical facility where a physical exam by a physician and a Clinical Chemistry panel will be performed to ascertain that they are healthy. Subjects will have mass resonance spectroscopy to measure Cho compounds in liver, and mass resonance imaging to assess fatty liver to validate the isotope dilution methodology and Fibroscan technology, respectively.

Intervention: Recruited subjects will be asked to fill out the Automated Self-Administered 24-hour Dietary Assessment Tool (ASA24) found on the NCI web site (<https://epi.grants.cancer.gov/asa24/>) for 3 days the week prior to the first diet intervention. This will estimate the choline intake level for subjects beginning the study. The week after screening, subjects will be placed on one of the three dietary choline levels (100%, 50%, and 25% - order randomly assigned) with a minimum 2 week washout between. On day 12 of each diet period, subjects will receive a 250mg bolus dose of the Cho delivered as Cho-d9 in order to estimate Cho pool sizes by isotope dilution (see Fig. 1, Appendix).

Follow-up: If the clinical laboratory data remain within normal values, this will conclude the subject's participation. If not, see section 4.3 (below).

Unscheduled Visits: Subjects may have to make unscheduled visits to pick up food if their freezer storage space is limiting.

3.2 Allocation to Treatment Groups and Blinding (if applicable):

All subjects will be randomly assigned to the order of the diet interventions. Investigators making metabolite, MRI, MRS, or Cho pool analyses will be blinded to diet assignments.

3.3 Study Duration, Enrollment and Number of Subjects:

The study lasts 10 weeks and a few days for each subject. We plan to enroll 150 subjects: 50 males, 50 pre-menopausal females, and 50 post-menopausal females. We will recruit an additional 30 subjects to account for drop out replacement, so the total number of subjects is 180.

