6.3 Statistical Methods

Statistical methods (Aim 1, SubAim 1a,1b). Unsupervised principal component analysis will first be used to examine the clustering of samples from the diet periods, and to ensure that the QC pool replicates center in the samples from which they were derived. This will enable the evaluation of the stability of the platform across the plate and between days for the signals which have not yet been assigned, to remove any signals that are too random and prevent the desired clustering, and to identify subjects who outlie from their perspective diet periods. Supervised Orthogonal Partial Least Squares Regression (OPLS-R) will then be used to identify a panel of biomarkers, assign weight to each biomarker, and calculate a composite score to predict choline pool size. When we applied Orthogonal Partial Least Squares Effect Projections (OPLS-EP) and Orthogonal Partial Least Squares Discriminant Analysis (OPLS-DA) to our previous data, we identified a panel of biomarkers and calculated a composite score that successfully predicted choline status (baseline or depletion) for both men and women (**Figure 1**). In this proposed study, we will use OPLS-R instead of OPLS-DA, because choline pool size is a continuous variable, while choline status in our previous study was a categorical variable. We will analyze all of the samples using OPLS-R to identify a panel of biomarkers that predicts choline pool size universally for all three diet periods (healthy men, pre- and postmenopausal women). We will also consider performing the analysis for each diet period separately in case the universal panel does not provide high accuracy in prediction. For the purpose of validation, we will not split samples into training and testing sets, as it reduces the number of samples used for model building. Instead, prediction error will be estimated using the Bootstrap method, which was found by recent studies as providing “nearly unbiased estimates of future model performance without holding back data when making the final estimates of model parameters” (101). Variable Importance to Projection (VIP)

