score will be calculated based on the OPLS weights and the variability explained in OPLS-R. Biomarkers with $VIP > 1.5$ will be considered the most important biomarkers responsible for prediction. Pathway analysis will be performed using GeneGo metacore (Thomson Reuters, <https://portal.genego.com>) and QIAGEN's Ingenuity Pathway Analysis (IPA®, QIAGEN Redwood City, www.qiagen.com/ingenuity).

Statistical methods (SubAim 1c). Linear model with repeated measures will be used to identify SNPs that increase (or decrease) the risk for developing choline deficiency-induced organ dysfunction. This analysis will be performed for each diet period (healthy men, pre- and postmenopausal women) separately. In each linear model, the choline status score defined by Aim 1 is the response variable. Diet effect (fixed), genotype effect (fixed), subject effect (random) and diet \times genotype interaction effect are the independent variables. In the repeated measures design, each subject serves as his/her own control. Therefore, confounding effect from genotype is not our concern. However, it is possible that genotype serves as a moderator, which interacts with the diet effect, and affects the direction or strength of the diet effect. For example, the change in choline status score in responding to dietary choline may be observed in subjects with one genotype (responders), but not in subjects with other genotypes (non-responders). The genotypes that modify the diet effect will be identified by the diet \times genotype interaction term. This analysis will be performed in the MIXED procedure in SAS (SAS Institute, Inc., Cary, NC). Benjamini-Hochberg method for False Discovery Rate (FDR) correction will be used for multiple testing correction. To improve the normality of the data, data transformation such as log transformation will be applied to metabolomics data, and outliers with studentized residue > 3 or < -3 will be excluded. Post hoc comparisons will be performed to identify metabolites associated with different levels of dietary choline and different genotypes. The analysis described above will also be applied to choline pool size data to identify significant diet \times genotype interaction effect for choline pool size.

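### The SubAim 1c crossover model has no period or previous-diet term, and no balancing of the diet orders is described

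*Combined protocol and SAP*

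**What the plan says.** The synopsis (Study Design), Sections 3.1 and 3.2 and Appendix Figure 1 describe a three-period crossover of the 100%, 50% and 25% diets. Section 3.2 states: "All subjects will be randomly assigned to the order of the diet interventions". It gives no method of randomisation and mentions no blocking or stratification. Each period is "followed by a minimum 2 week washout period". What subjects eat in the washout is not stated.

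Section 6.3 lists the terms of the SubAim 1c model: "Diet effect (fixed), genotype effect (fixed), subject effect (random) and diet" × genotype. It is fitted separately in men, premenopausal women and postmenopausal women, first with the choline status score and then with choline pool size as response. No period, sequence or previous-diet term appears, and no check for carry-over is planned.

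The primary analysis is different in kind: "We will analyze all of the samples using OPLS-R to identify a panel of biomarkers that predicts choline pool size universally".

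On recovery, Section 1.1 reports that most metabolite changes "were at least partially corrected by Cho repletion". Section 1.3 says that clinical liver and muscle damage was "reversed with 2 weeks of feeding 100% Cho diet".

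Section 8 contradicts the random order. It says that there is no randomisation and that every subject starts on the 100% diet.

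**The concern.** Two separate things can disturb a within-subject diet contrast. One is drift over the three periods (season, assay batch, habituation). The other is carry-over from the preceding diet. The planned model allows for neither.

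Drift matters only so far as diets and periods are unevenly matched. With unrestricted allocation they will be somewhat uneven within a group of about 50, and more so within a genotype subgroup of it. Carry-over does not average out, because the 25% period tends to follow richer diets and the 100% period poorer ones, so it pulls the contrast towards zero. Section 1.3 supports 2-week reversal of organ damage on a 100% diet, but it does not address the metabolites that make up the score.

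At stake are the diet effect and the diet × genotype interaction in SubAim 1c. That interaction carries the only power figure in the plan (Section 6.4).

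**Working it through.** **The plan's own figure.** Section 6.4 gives 89.61% power for an interaction effect of 0.6 at P<0.05, without n, SD, genotype split or sidedness, so it cannot be uniquely reproduced. A two-sided two-group comparison within one group of 50 gives 0.45 to 0.56. Pooling 150 subjects with an assumed 74/26 split gives 0.897. Nothing below depends on this figure, except the one power illustration under carry-over.

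**Drift.** Let d be a subject's period number on the 25% diet minus that on the 100% diet. Over the six orders, d is ±1 in four and ±2 in two, so its mean is 0 and its variance is (4×1 + 2×4)/6 = 2.

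- n = 50: SD of mean d = √(2/50) = 0.20 periods (95% limit about 1.96 × 0.20 = 0.39).
- n = 150: √(2/150) = 0.12.
- Interaction, taking the 56%/44% split that Section 5.1 expects in premenopausal women (28 and 22 of 50): √(2/28 + 2/22) = 0.40 periods.

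The error in the estimate is this imbalance multiplied by the drift per period. The mean imbalance is zero, so there is no average bias. The documents give no estimate of drift.

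**Cost of a period term.** With balanced orders (n = 48), the variance of the 25% versus 100% contrast is 2σ²/48 = 0.0417σ² with or without period. In a diet-only model the residual degrees of freedom fall from 94 to 92.

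**Recovery.** Appendix Figure 3 gives depletion/baseline (D/B) and repletion/depletion (R/D). Their product approximates repletion/baseline.

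| Marker | Fatty liver | Muscle dysfunction |
|---|---|---|
| Betaine | 0.45 × 1.66 = 0.75 | 0.53 × 1.07 = 0.57 |
| Sarcosine | 0.47 × 2.00 = 0.94 | 0.60 × 1.08 = 0.65 |
| Dimethylglycine | 0.51 × 1.81 = 0.92 | 0.55 × 1.41 = 0.78 |
| Homocysteine | 1.16 × 0.97 = 1.13 | 1.19 × 0.99 = 1.18 |
| Choline | 0.67 × 1.50 = 1.01 | 0.66 × 1.25 = 0.83 |
| Phosphatidylcholine | 0.89 × 1.08 = 0.96 | 0.90 × 1.06 = 0.95 |
| Methionine | 0.86 × 1.10 = 0.95 | 0.93 × 1.01 = 0.94 |

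Subjects without dysfunction have no repletion value (NA).

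**Size of carry-over.** Assume that a fraction c of each diet effect persists into the next period. Over the six orders each diet comes first twice and follows each other diet twice. Carry-over therefore adds (c/3)(τ50 + τ100) to the 25% mean and (c/3)(τ50 + τ25) to the 100% mean. The observed contrast is (1 − c/3)(τ25 − τ100).

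- c = 0.1: shrinkage of 3%.
- c = 0.3: shrinkage of 10%.

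A period term leaves this unchanged. A previous-diet term removes it, but raises the contrast variance from 0.0417σ² to 0.0521σ² (0.0521/0.0417 = 1.25). If the interaction took that whole loss, 89.6% power would fall to about 82%: (1.96 + 1.26)/√1.25 − 1.96 = 0.92, and Φ(0.92) = 0.82.

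**The case against.** The strongest reply is that a random order already protects the diet contrast from drift on average, that the carry-over evidence is thin, and that the model serves only a secondary aim. Much of this stands.

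- A reader might infer from Figure 3 that two weeks is too short here. The documents do not show that. The table follows a 10% diet for up to 7 weeks, against 25% or 50% for 2 weeks in this study, and the synopsis expects smaller changes. Repletion data exist only for subjects with dysfunction. The products multiply group ratios, and background food may have differed: stachydrine, listed under diet, gives 0.06 × 5.39 = 0.32 and 0.10 × 0.86 = 0.09.
- A reader might infer that the washout is on self-chosen food. Food pick-ups are listed only for diet days, so this is plausible, but the diet is simply unspecified. Section 4.2 also mentions a 3-day supply of the 100% diet at Visit 1, whose role is unclear. Nor does low usual intake ("only 11% of adult Americans achieve the Adequate Intake level of Cho") show a failed washout, since Section 3.1 brings subjects into the first period from their usual intake too. What matters is a return to the same starting state.
- A reader might infer that adding period cures incomplete recovery. It does not.
- A reader might infer that period-start values are already available for adjustment. Blood is drawn then, but only clinical chemistry is planned on it (Sections 1.3 and 5.1). Pool size needs the labelled dose, so it has no period-start value.
- The Aim 1 model relates markers to pool size measured in the same period. Carry-over disturbs that association only if the two recover at different rates.

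What the reply does not answer is that the model omits a standard crossover term that costs almost nothing, and that the plan offers no means of seeing whether carry-over occurred.

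**Conclusion.** The point holds for SubAim 1c, as a modest and cheaply corrected gap. Omitting period adds chance error, not average bias. The imbalance SD is 0.20 periods for a diet contrast at 50 per group and about 0.40 for an interaction with a 56/44 split, multiplied by a drift of unknown size. These figures assume unrestricted allocation, inferred from the absence of any described blocking.

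Carry-over is a separate risk that the documents neither establish nor exclude. Under an assumed 10% to 30% it would shrink the 100% versus 25% contrast by 3% to 10%. If recovery differed by genotype, the interaction would be distorted as well.

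All of this presumes the random order. Under the fixed order in Section 8, period is largely confounded with diet, and neither a period term nor blocking would repair it. The documents do not support extending the criticism to the Aim 1 prediction model, beyond the case of unequal recovery rates.

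**What to change.** First reconcile Section 8 with the synopsis, Sections 3.1 and 3.2 and Appendix Figure 1. If the random order is confirmed:

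1. Add period as a fixed effect to the SubAim 1c models for both score and pool size. This costs 2 degrees of freedom. The contrast variance is unchanged when orders are balanced.
2. Assign the six diet orders in permuted blocks within each of the three groups, and describe the method in Section 3.2. This costs a blocked list. Dropout and genotype will still leave some imbalance, which the period term absorbs.
3. Pre-specify a sensitivity model with a previous-diet term and, for the interaction, its product with genotype. It needs no new assays. The variance rises by about 25%, so it should not be the main analysis.
4. Use period-start biomarker values only where they are assayed. Running the panel on those samples would be an added cost, and it cannot be done for pool size.
5. State in the protocol what the washout diet is, so that the carry-over results can be interpreted.
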